Protocol

Evaluation of the diagnostic value of TOF-18F-FDG PET/CT in patients with suspected pancreatic cancer

September 2013

Content

Summary.....	2
Background information.....	4
Study hypothesis.....	6
Aim of the study.....	6
Study process.....	7
Patients.....	8
Patient recruitment.....	8
Protocol: PET/CT.....	9
Data handling.....	10
References.....	11

Summary

According to the application for the responsible ethics committee of the Medical University of Graz a study is to be performed for the „*evaluation of the diagnostic value of TOF-18F-FDG PET/CT in patients with suspected pancreatic cancer*“.

The essential idea of the study is the analysis of the use of early (30min p.i.) and delayed (90min p.i.) imaging as well as a diagnostic CT of the abdomen with contrast medium and pancreas protocol for characterization of pancreatic masses with TOF (Time-of-Flight)-18F-FDG-PET/CT.

According to current scientific evidence, there are no studies in the literature regarding the characterization of pancreatic masses by the "Time-of-Flight"-technique (TOF) within PET/CT. Usually, the differentiation between chronic pancreatitis and pancreatic carcinoma is often not possible. Likewise, the differentiation of the pancreas from surrounding anatomical structures (duodenum) in PET/CT with low dose CT is often not possible. An exact diagnosis of a possible malignancy or benignancy, as well as the precise anatomical localization of the detected lesion, is however of decisive importance for the further therapeutic procedure [1-4]. If a benign lesion is present, an extensive operation (Whipple operation) may not be necessary.

As a rule, patients with suspected pancreatic cancer are assigned to the Division of Nuclear Medicine for 18F-FDG PET-CT imaging. Early (30min p.i.) and delayed images (90min p.i.) are taken to better distinguish between malignant from inflammatory lesions. After the PET/CT examination, a TOF-reconstruction is performed, which does not require the presence of the patient, but improves the image quality to differentiate the lesion in the pancreas better. For better anatomical demarcation of the pancreas of adjacent structures (duodenum) additionally a diagnostic CT of the abdomen (up to the iliac crest) with pancreas protocol (2 phases) with i.v. administration of iodine-containing contrast medium (Visipaque®) and oral administration of a negative contrast medium (500 ml water) for intestinal distension is additionally performed. After consultation with the referring physician, it must be ensured for reasons of radiation hygiene that the patients do not have a diagnostic CT with contrast agent before the PET/CT examination. If this is not possible, a diagnostic CT of the upper abdomen (up to the lower liver margin) is performed with pancreas protocol with 2 phases (arterial and portal venous). In most cases these patients are operated, only in the rarest of cases, a biopsy/brush swab is carried out beforehand. The histopathological preparation of the surgical specimen is then performed. These steps are routine. This approach is to be retained in the project. These steps are

- 1) Assignment of the patient to the TOF-PET-CT (with images 30min und 90min p.i.)
- 2) Performing a diagnostic CT of the abdomen with parenteral and oral contrast media and pancreas protocol as part of the PET/CT examination
- 3) Routine performance of the operation/fine needle puncture
- 4) Routine histopathological evaluation

With the help of the enclosed Informed Consent, the patient's information and written consent are duly given. Furthermore, in the case of administration of parenteral contrast medium, the relevant information is routinely provided using a contrast medium information sheet.

The administration of parenteral contrast media is performed according to the ESUR Guidelines [1].

Background information

Several studies dealt with the question of differentiating between benign and malignant processes of the pancreas using 18F-FDG PET/CT imaging. However, a reliable statement can currently only be made by histopathological assessment (considered the gold standard). For this reason, a priori no conclusion can currently be drawn as to the malignancy or benignity of the lesion in question. According to recent studies, malignant pancreatic diseases occur in patients with suspected pancreatic carcinoma and condition after pancreateoduodenectomy or fine needle aspiration with a frequency of 66-81% (47-78% of which are adenocarcinomas), benign diseases with a frequency of 19-34%, of which about 60% are inflammatory diseases and 40% benign cystic tumors [2-5].

In this study, patients with suspected benign diseases that are not operated and do not have a fine needle biopsy and are only monitored by radiological follow-ups are excluded.

According to the current status of science, there are no studies in the literature concerning the characterization of pancreatic lesion expansions using the "Time-of-Flight"-technique (TOF) in the framework of PET/CT. The TOF technique is a new reconstruction algorithm in PET/CT that can only be applied to newer devices. High-definition PET technology can significantly improve spatial resolution (to 2 mm) and increase sensitivity (TOF) by a factor of 3. The combination of both techniques (HD-PET with TOF) is called Ultra HD-PET.

The 18F-FDG PET/CT is indicated for staging in patients with suspected pancreatic carcinoma and was also classified as 1a indication for differentiation between inflammation and pancreatic carcinoma according to the 3rd German Interdisciplinary Consensus [6]. In patients with suspected pancreatic carcinoma, diagnosis is often only possible with difficulty due to the limited anatomical assignment of small focal lesions and discreetly increased tracer-uptake, differentiation between benign and malignant is often not possible, i.e., differentiation between chronic pancreatitis and a malignant process is often only possible to a minimal extent. According to clinical studies [7;8;21-26], the TOF-technique and additional i.v. administration of iodine-containing contrast medium and oral administration of a negative contrast medium can significantly improve the sensitivity and anatomical differentiation of the target organ from adjacent structures. However, this technique has not yet been used in patients with suspected pancreatic cancer.

Another already established method to better distinguish inflammatory from malignant lesions in PET/CT is to take images at two different time points and to compare the Standard Uptake Value (SUV), a measure of regional accumulation intensity, at these two times [3;17;18]. Here an increased FDG-uptake already in the early images is classified as benign/inflammatory, and an increase in FDG -

uptake in the delayed images is classified as malignant. A missing FDG uptake both in the early and the delayed images is considered benign.

The diagnostic procedure of 18F-FDG PET is based in case of oncological questions on the mechanism that tumor cells show an increased glucose metabolism and that these areas become visible in nuclear medical imaging through increased 18F-FDG tracer uptake. The SUV has established itself as a semi-quantitative measure of uptake concerning patient weight (SUV/bw), which is used both for staging and for determining tumor boundaries [3;9-14;17-20;21;27-31]. For further curative as well as palliative treatment, knowledge of the exact tumor boundaries is essential for the further treatment steps. On the one hand, these are needed for measurement and differentiation (from vital structures) as well as for planning (knowledge of the exact tumor size) in further treatment [32-34]. To date, CT and MRI have mainly been used as morphological methods to delimit tumors and to assess the resectability, whereby functional imaging often plays a decisive role in therapy decisions but is currently hardly taken into account for the problems of delimitation and resectability.

PET/CT is routinely performed in the suspected case of pancreatic cancer [6-20]. Subsequently, a subtotal pancreaticoduodenectomy (Whipple operation) with lymphadenectomy is performed routinely in cases of urgent suspicion of malignancy and PET scintigraphically confirmed absence of distant metastases. Thereby in addition to the pancreatic head and the duodenum the gall bladder, distal bile duct, and gastric antrum are removed. At the University Clinic for Surgery Graz, a previous sonographic or CT-controlled biopsy is usually not performed due to the danger of sten canal metastases in the case of resectable tumors. If necessary, a diagnostic laparotomy is performed. Even a negative fine needle puncture that may have been performed beforehand does not rule out an operation. However, in the rare case of a CT-guided biopsy alone without subsequent surgery, such patients should also be included in the present study. PET as well as the operation/fine needle puncture are routine clinical procedures and are therefore not explained further.

In the area of pancreatic lesions, it is difficult to distinguish adjacent anatomical structures (duodenum). For this reason, in the present study additionally, a parenteral iodine-containing (Visipaque®) and a negative oral contrast medium (500 ml water) will be administered. One difficulty of such studies is that the dignity of the tumor can only be determined after histopathological examination of the surgical specimen.

Study hypothesis

Early- (30min p.i.) and delayed images (90min p.i.), diagnostic CT of the abdomen with contrast medium and Time-of-Flight (TOF)-reconstruction within the framework of 18F-FDG PET/CT allow an improvement in the differentiation of malignant from benign lesion expansions of the pancreas.

Aim of the study

[figure not shown]
The aim of the study is to improve the differentiation between malignant and benign lesions in the pancreas in patients with suspected pancreatic cancer by images 30min und 90min p.i. and a diagnostic CT of the abdomen with contrast medium in the context of TOF-18F-FDG PET/CT and thus to improve the quality of PET/CT findings. Also, a cut-off value of SUV will be determined in correlation with the histopathological results to better differentiate between malignant and benign lesions of the pancreas.

Study process

Assignment with suspected diagnosis

Legend:

- grey: routine examination
- blue: study-specific work steps

Patients

118 patients are to be diagnosed continuously according to protocol.

Inclusion criteria:

- patients with suspected pancreatic cancer (morphologically suspect)
- operation/fine needle puncture

PET/CT examination with TOF-reconstruction algorithm and contrast medium:

- sober
- plasma glucose level < 140 mg/dl
- position capability
- checking of:
 - creatinine value < 1.2 mg/dl (for values >1.2 mg/dl
no administration of contrast medium) and eGFR-value > 45 ml/min/1.73 m²
(for values < 45 ml/min/1.73 m² no administration of contrast medium)
 - TSH-value 0.1-4.0 µU/ml (for values <0.1 µU/ml
no administration of contrast medium)

Exclusion criteria:

- patients under 18 years
- plasma glucose level > 140 mg/dl
- patients with histopathologically confirmed distant metastases at the time of PET/CT examination
- patients with non-pancreatic tumors
- patients, who **will not undergo surgery** or had **no fine needle puncture (FNP)** and therefore have no histopathological findings of the pancreas
- pregnancy

Patient recruitment

As a rule, the patients are referred to the Division of Nuclear Medicine for diagnostic staging using 18F-FDG PET/CT. As part of the preparation of the patients for the PET/CT examination, the principle investigator and other staff members will provide the information, and in case of participation at the study, the Informed Consent (enclosed) will be signed.

Protocol: PET/CT

After the patients have been admitted to PET/CT operation/fine needle biopsy must be performed within a maximum of 4 weeks.

Patient preparation

- Blood sugar control < 140 mg/dl
- Administration of the tracer in the PET application room

Application

- Intravenous injection of maximal 370 MBq 18F-FDG (fluorodeoxyglucose)
 - depending on the body weight (according to EANM European Dose-Card corresponds to approx. 7mSv patient dose)

Patient preparation

- Rest for 30 minutes (tempered and darkened) while oral administration of 500 ml water (negative contrast medium)
- Immediately before the start of the examination empty the bladder as thoroughly as possible
- Remove all metallic objects from the test area to avoid artifacts
- Comfortable supine position of the patient during acquisition

Examination device

- Siemens Biograph mCT 40

Protocol

- CT according to 120kV 50mAs eff. (scout, quality standard low dose)
- Whole body (skull base to thigh): static acquisition of 6 bed-positions (depending on patient size) of 2 minutes each (with BMI >30 acquisition time extend by 1 minute per position)
- 90min p.i. image (abdomen): static image of 2-3 bed-positions (depending on patient size) at 2 minutes each (with BMI >30 acquisition time extend by 1 minute per position)

Image evaluation, SUV-calculation

- Evaluation station: Siemens SYNGO MMWP

Work area

- University Clinic of Radiology, Division of Nuclear Medicine, room 440/438, 4th floor

Protocol diagnostic CT of the abdomen with pancreas protocol and contrast medium

Examination device

- Siemens Biograph mCT 40

Protocol

- CT according to 120kV 220mAs in spiral mode (according to a standard dose length product of approx. 450 resp. 225 mGy cm, corresponding to approx. 6.7 mSv patient dose with diagnostic

CT to the iliac crest or approx. 3.3 mSv with diagnostic CT to the lower liver margin). The dose length products were derived from measurements on the patient and the phantom.

- Reconstruction to 5mm layer thickness with an increment of Schichtdicke 3 mm

Statistical Analysis Plan (SAP)

Evaluation of the diagnostic value of TOF-18F-FDG PET/CT in patients with suspected pancreatic cancer

Principal Investigator	[name] Specialist in Nuclear Medicine Medical University of Graz Department of Radiology, Division of Nuclear Medicine
Protocol Identification Number	Protocol TOF-P V1 (dated 2013-09-25)
Document Date	31.03.2019
Version	Draft 0.1

Abbreviations

AUC	Area under the curve
CT	Computed tomography
FDG	Fluorodeoxyglucose
p.i.	post injectionem
PET/CT	Positron emission tomography/computed tomography
ROC	Receiver operating characteristic
SUVmax	Maximum Standard Uptake Value
TOF	Time-of-Flight
TSH	Thyroid stimulating hormone

Table of contents

1. Introduction.....	4
2. Study design.....	4
2.1 Sample size planning.....	5
3. Aims and objectives.....	6
4. Outcomes.....	6
4.1 Primary outcome.....	6
4.2 Secondary outcome.....	6
5. Population to be analyzed.....	6
6. Analyses.....	6
6.1. Primary outcome.....	6
6.2 Secondary outcome.....	7

1. Introduction

[figure not shown]
The study aims to improve the differentiation between malignant and benign lesions in the pancreas in patients with suspected pancreatic cancer by images 30min und 90min p.i. and a diagnostic CT of the abdomen with contrast medium in the context of TOF-18F-FDG PET/CT and thus to improve the quality of PET/CT findings. Also, a cut-off value of SUV (primary outcome measure) will be determined in correlation with the histopathological results to better differentiate between malignant and benign lesions of the pancreas. Secondary outcome measures are the better demarcation of pancreatic lesions of the adjacent anatomical structures as well as the tumor size.

2. Study design

Study subjects will be recruited from the patients with suspected pancreatic cancer who are referred to the Division of Nuclear Medicine for diagnostic staging using 18F-FDG PET/CT. As part of the preparation of the patients for the PET/CT examination, [name] and other staff members will provide the information, and in case of participation at the study, the Informed Consent (enclosed) will be signed. Patients had to be sober and should have a plasma glucose level < 140 mg/dl. Furthermore, the creatinine level < 1.2 mg/dl (for values >1.2 mg/dl no administration of contrast medium) and TSH level (for values <0.1 µU/ml no administration of contrast medium) will be checked.

The study is a prospective single-center clinical trial with one arm. During this clinical study at intervals of 4 weeks, the following examinations will be performed: PET/CT-examination, surgery or fine needle puncture. If the patients do not have a fine needle puncture or surgery, they are automatically excluded from the study due to missing histopathological findings. The study design is shown in Figure 1 below.

Figure 1 Flowchart of screening and inclusion process

2.1 Sample size planning

One hundred eighteen patients would be required to demonstrate an improvement in specificity of 25% (to 70%) with the new method assuming a specificity of the current method of 45% at a prevalence of malignant lesions of 70% (corresponding to 30% benign lesions). The calculation of these values is based on a formula that selects the sample size so that the lower limit of the 95% confidence interval by the expected specificity of the new method most probably exceeds the specificity value of the current method, i.e., the confidence interval no longer contains this value. With a power of (in this case) 90%, you can say that the specificity of the new method is higher than the old one.

3. Aims and objectives

The aim of the study is to analyze if 30 and 90min p.i. images and a diagnostic CT of the abdomen in the context of TOF-18F-FDG-PET/CT can improve the differentiation between malignant and benign lesions in the pancreas in patients with suspected pancreatic cancer.

4. Outcomes

This section will present the outcomes investigated to answer the study aims and objects. The analyses are described in section 6 Analyses.

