6.1 Primary outcome

The primary analysis will compare the SUVmax values of all detected pancreatic lesions in the PET/CT images 30 and 90min p.i. with and without TOF using ROC-analysis. AUC values with and without TOF 30 and 90min p.i. will be compared using the DeLong-test. Sensitivity and specificity of SUVmax of each imaging modality (with and without TOF) in correlation with the

histopathological results will be calculated. Furthermore, a cut-off value of SUVmax for differentiating malignant and benign pancreatic lesions will be computed using ROC-analysis. Besides, sensitivity, specificity, diagnostic accuracy and the positive and negative predictive value of the results of the PET/CT findings in correlation with the histopathological results will be calculated.

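### SAP 2.1 sizes the trial for specificity above a fixed 45%, but SAP 6.1 never makes that comparison, so the stated 90% power belongs to no planned analysis

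*SAP*

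**What the plan says.** **Sizing.** SAP 2.1 takes 45% as the specificity of the current method, 70% as that of the new one, and 30% benign. The criterion behind the sample size reads: "lower limit of the 95% confidence interval by the expected specificity of the new method most probably exceeds the specificity value of the current method". The section then states: "With a power of (in this case) 90%, you can say that the specificity of the new method is higher than the old one".

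**Analysis.** SAP 6.1 opens differently: "The primary analysis will compare the SUVmax values of all detected pancreatic lesions" at 30 and 90 minutes, with and without TOF, by ROC analysis. Its one hypothesis test is this: "AUC values with and without TOF 30 and 90min p.i. will be compared using the DeLong-test". Specificity is then to be calculated for SUVmax with and without TOF. A threshold comes from the same data: "a cut-off value of SUVmax for differentiating malignant and benign pancreatic lesions will be computed using ROC-analysis". A further set of accuracy measures follows: "Besides, sensitivity, specificity, diagnostic accuracy and the positive and negative predictive value of the results of the PET/CT findings", again against histology.

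**Elsewhere.** SAP 4.1 names SUVmax (two time points, with and without TOF) as the primary outcome, and the SAP Introduction calls an SUV cut-off the primary outcome measure. The same Introduction gives as an aim "thus to improve the quality of PET/CT findings". SAP 6.2 adds a McNemar test on the number of patients with increased uptake and a t-test on SUVmax. The Protocol gives the 118 but has no statistical section.

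**The concern.** A sample size with stated power is a promise about a particular comparison. Here the comparison appears only in the sizing section. Someone who follows SAP section 6 to the letter will produce ROC curves, DeLong p-values and several specificity estimates, but will not test the one claim that the trial was sized for.

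Two things then go wrong. First, if someone sets a specificity against 45% at the reporting stage, they must choose among several readings with the results in view. Second, a reader may carry the 90% over to the DeLong result, for which it was never derived.

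**Working it through.** **1. Reproduce the 118.** Inputs from SAP 2.1: reference 0.45, expected 0.70, two-sided 95% interval (z = 1.960), power 90% (z = 1.282), benign share 0.30.

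- Benign needed = (1.960 + 1.282)² × 0.70 × 0.30 / (0.70 − 0.45)² = 35.3
- Total = 35.3 / 0.30 = 117.7, rounded up to 118
- Check: with 0.30 × 118 = 35.4 benign, SE = √(0.21/35.4) = 0.0770, and power = Φ(0.25/0.0770 − 1.960) = 90.1%

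The plan's figure is therefore a one-sample Wald comparison with a fixed 45%. Sizing two independent proportions would need 81 benign per group, so that is not what was done.

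**2. Look for that comparison in section 6.**

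| Element of the 2.1 rule | In SAP 6.1? |
|---|---|
| Specificity estimate | Yes, for several readings |
| 95% confidence interval, with method | No |
| Comparison with 45% | No |
| Which reading is the new method | Not stated |
| Rule for a positive PET/CT finding | Not stated in section 6 |

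The only classification rule is in the Protocol background, which contrasts early with delayed uptake and adds: "A missing FDG uptake both in the early and the delayed images is considered benign". It is not carried into the SAP. The SAP 6.2 tests do not concern specificity.

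**3. Can the 90% be transferred to DeLong?** The documents give no AUC, AUC difference or correlation, so its power cannot be derived from them. For illustration only, assume 83 malignant and 35 benign, Hanley–McNeil variances, baseline AUC 0.70–0.80, correlation 0.5–0.9 and two-sided 5%. Power is then about 9–40% for an AUC gain of 0.03, 18–80% for 0.05, and 59–99.9% for 0.10. Four AUCs allow six pairwise contrasts. The two natural ones are TOF against non-TOF at each time point, and neither is named as primary.

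**4. Power of the 2.1 rule by enumeration.** For each possible benign count n, sum the binomial probabilities (true specificity 0.70) of the outcomes whose lower 95% limit exceeds 0.45. Then average over n ~ Binomial(118, q). The values of q are the SAP's 30% and the ends of the 19–34% benign range in the Protocol background.

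| Benign share q | Expected benign | Wald | Wilson | Exact |
|---|---|---|---|---|
| 19% | 22.4 | 70.2% | 67.1% | 59.3% |
| 30% | 35.4 | 86.7% | 86.0% | 81.4% |
| 34% | 40.1 | 90.2% | 89.8% | 86.3% |

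The interval method, which the SAP does not name, moves power by about 5 points at 30% benign.

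**5. If the reading were SUVmax at a same-data cut-off.** The SAP does not say how the cut-off is picked from the ROC curve. Assuming Youden's index, equal-variance binormal data and 83 against 35 patients, simulation gives apparent specificity about 5–7 points above true specificity at AUC 0.70–0.85. The 2.1 calculation makes no allowance for this.

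**The case against.** The strongest reply is that SAP 2.1 and 6.1 belong to one document. Section 2.1 already fixes the 95% level, the 45% benchmark and the direction, and 6.1 already plans specificity, so an analyst needs only a cross-reference. Part of this stands: the gap is narrow, and nothing in the SAP says that a reading will be picked after the results are known. That is a risk, not a plan. But a cross-reference alone would not make the rule executable, because it would not say which specificity is meant, how a finding is called positive, or which interval applies.

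Several stronger inferences are tempting, and the documents do not support them:

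- *The sample size is wrong.* It is not; 118 follows from its stated inputs, and 30% benign lies within the Protocol's cited range.
- *The PET/CT findings are plainly the new method.* The aim of better findings points that way, but the Introduction and SAP 4.1 name SUV as primary. The documents leave it open.
- *The DeLong test is underpowered.* Its power is unknown.
- *The unit changes from patient to lesion.* SAP 2.1 itself speaks of the prevalence of lesions, 4.1 refers to a single lesion, and 6.2 counts patients. This suggests one lesion per patient, so it is a wording point to clarify.
- *A formal sensitivity criterion is required.* The 2.1 rule does cover specificity alone: a reading unrelated to histology that calls 30% of patients positive would meet it in 86% of trials (Wilson, 30% benign). But the documents set no sensitivity target, and 6.1 already reports sensitivity, where such a reading would show. A formal condition is optional.

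**Conclusion.** The point holds as a mismatch between sizing and analysis. The 90% is attached to a one-sample specificity rule that section 6 does not contain, and the test that section 6.1 does contain has neither stated power nor a primary contrast. The match of 117.7 to 118 settles what was sized.

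The numerical shortfall in the 90% is secondary. At 30% benign it is about 3 to 9 points, depending on the interval. The fall to 59–70% applies only if the benign share is as low as 19%. These figures assume a true specificity of 70%, a prespecified positivity rule, one result per patient and histology for all 118. The 5–7 point overstatement depends further on the assumed Youden cut-off and binormal data, and matters only if SUVmax at a same-data cut-off is the chosen reading.

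The mismatch should be resolved before the data are analysed, since a choice made afterwards cannot be shown to be independent of the results. The SAP is labelled Draft 0.1.

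**What to change.** 1. **SAP 6.1, before analysis.** The sponsor names the one reading that is the new method: either the PET/CT findings, or SUVmax at a stated time point with TOF. State its positivity rule, including how a lesion without uptake counts, and take one result per patient. Add its specificity in histologically benign patients with a named 95% interval (for example Wilson), and define success as a lower limit above 45%. Report sensitivity with its 95% interval beside it. If the reading is SUVmax at a cut-off chosen by ROC in the same data, report an optimism-corrected specificity (bootstrap or cross-validation) and do not attach the 90% to the apparent value.
2. **SAP 2.1.** Say that 90% is a Wald approximation at exactly 30% benign and covers specificity alone. Give the enumerated power for the chosen interval (about 86% for Wilson) and its value at 19% benign (67% for Wilson).
3. **DeLong.** Name one contrast, TOF against non-TOF at one time point, as the primary AUC test and treat the other as secondary. State that 118 was not derived for it.
4. **Unit.** Clarify in 6.1 whether a patient can contribute more than one lesion and, if so, how these reduce to one result.

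Cost: no extra patients or scans. A few decisions must be fixed in writing before analysis, and the stated power becomes slightly less favourable.

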4.3 Safety outcomes

Adverse events

Possible adverse events are reported in the case report form.

Concomitant medications

Usage of diabetes or thyroid medications before PET/CT examination will be recorded.

5. Populations to be analyzed

There is only one population in this clinical trial. All patients undergo a TOF-18F-FDG PET/CT examination with images 30 and 90min p.i. with a diagnostic CT of the abdomen. In all patients exist PET images with and without TOF.

6. Analyses

All outcomes will be presented using ROC-analysis or descriptive statistics. SPSS version 25 and R will be used for all statistical analysis.

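### Exceeding a fixed, unsourced 45% cannot show that the new method is more specific than the old one, and no paired comparison of specificity is planned

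*SAP*

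**What the plan says.** SAP 2.1 states "One hundred eighteen patients would be required" to "demonstrate an improvement in specificity of 25% (to 70%) with the new method". The comparator enters only as a planning value, "assuming a specificity of the current method of 45" per cent, and the benign share is set "at a prevalence of malignant lesions of 70% (corresponding to 30% benign lesions". The criterion is that the "lower limit of the 95% confidence interval by the expected specificity of the new method most probably exceeds" the value for the current method. The section then draws its conclusion: "With a power of (in this case) 90%, you can say that the specificity of the new method is higher than the old one".

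Neither document gives a source or an uncertainty for the 45%, or says what the current method is.

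SAP section 5 says: "In all patients exist PET images with and without TOF". SAP 6.1 compares the AUCs with and without TOF by the DeLong test and calculates sensitivity and specificity for each image set. SAP 6.2 applies the McNemar test to the number of patients with increased uptake, as a measure of demarcation. No section gives a test or a confidence interval for a difference in specificity.

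**The concern.** The criterion in 2.1 is a one-sample rule: one observed proportion against a constant. The conclusion is a two-method statement. It follows only if the old method's specificity in these patients is 45% or less.

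There is reason not to take that for granted. Specificity depends on which benign lesions enter the sample. The protocol (Background information; Exclusion criteria) excludes patients without surgery or fine needle puncture, including those with suspected benign disease who are only followed radiologically. A specificity taken from elsewhere need not hold in the benign patients who remain.

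The error can go either way. If the old method does better than 45% here, the rule can declare a gain that does not exist. If these benign lesions are harder to classify, a real gain can be missed. Specificity is the only quantity the sample size rests on, so a reader of the results would expect the trial to answer this question.

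**Working it through.** **Inputs from SAP 2.1.** New method 70%; current method 45%, fixed; 95% confidence interval (two-sided 5%); power 90%; 30% benign; 118 patients.

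**Reproducing 118.** One proportion against a constant, with the variance taken at 70%:

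- benign patients = (1.96 + 1.2816)² × 0.70 × 0.30 / 0.25² = 10.508 × 0.21 / 0.0625 = 35.3
- total = 35.3 / 0.30 = 117.7, rounded up to 118

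The figure reproduces. The formula has no term for sampling error in the old method.

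**What the rule requires.** 118 × 0.30 = 35.4, so take 35 benign patients. Lower 95% limits:

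| Correct benign calls | Wald | Wilson | Clopper-Pearson |
|---|---|---|---|
| 21 of 35 | 0.438 | 0.436 | 0.421 |
| 22 of 35 | 0.468 | 0.463 | 0.449 |
| 23 of 35 | 0.500 | 0.492 | 0.478 |

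The rule needs 22 correct with Wald or Wilson and 23 with Clopper-Pearson. The SAP does not say which interval applies.

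**How often the rule is met.** P(X ≥ 22) or P(X ≥ 23), with X binomial(35, true specificity of the new method):

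| True specificity, new method | 22 needed | 23 needed |
|---|---|---|
| 45% | 2.6% | 1.1% |
| 50% | 8.8% | 4.5% |
| 60% | 43.6% | 30.6% |
| 65% | 67.6% | 54.2% |
| 70% | 86.5% | 77.3% |

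These probabilities do not depend on the old method. The true values in the next two checks are assumptions; the documents give none for this cohort.

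- *No gain.* If the old method also has 60%, 65% or 70%, the last three rows are the rates of a false declaration of higher specificity. An exact two-sided McNemar test in the same 35 patients would favour the new method in at most 1.5% of trials with no gain (discordance 10% to 50%).
- *Real gain, harder sample.* If the old method has 30% and the new 50%, the rule is met in 8.8% (4.5% with Clopper-Pearson).

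**Exact McNemar power, 35 benign patients.** Let p01 be the share of benign patients called correctly only by the old reading, and p10 = gain + p01 the share called correctly only by the new one. The number of discordant pairs d is binomial(35, p10 + p01). Given d, the number favouring the new reading, b, is binomial(d, p10/(p10 + p01)). The test favours the new reading when b > d − b and 2 × P(Bin(d, 0.5) ≥ b) ≤ 0.05. The documents give no discordance, so p01 is assumed.

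| Assumed gain | p01 = 0 | p01 = 0.05 | Independent readings |
|---|---|---|---|
| 30% to 50% | 73% | 49% | 31% (p01 = 0.30 × 0.50 = 0.15) |
| 45% to 70% | 90% | 66% | 47% (p01 = 0.45 × 0.30 = 0.135) |

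Hand check for p01 = 0: six discordant pairs, all favouring the new reading, give p = 2 × 0.5⁶ = 0.031, while five give 0.0625. Power is therefore P(Bin(35, 0.25) ≥ 6) = 90% for the larger gain.

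**The case against.** The strongest reply has four parts.

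*The image without TOF is not the old method.* A reader might infer that the 45% belongs to the image without TOF, and that the rule would credit TOF with a gain it did not make. The documents do not support this. The study hypothesis defines the new approach as early and delayed imaging plus contrast CT plus TOF, and 2.1 attributes the gain to the new method as a whole. The protocol describes TOF as a reconstruction made after the examination without the patient, so the image without TOF shares the dual-time imaging and the contrast CT. A comparison with and without TOF isolates one component and cannot by itself show superiority over the old method. This stands and limits the remedy.

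*The 45% is a planning value, not an analysis rule.* A reader might infer that the trial will be judged against 45%. Section 6 contains no such check, and a fixed benchmark is a common way to size a one-arm study. This also stands. The rates above describe the inference that 2.1 licenses, not a listed analysis. But the sentence in 2.1 says what may be concluded, and that is the part that fails.

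*A within-patient comparison is already planned.* True for AUC. AUC summarises all thresholds, so the DeLong test cannot support a statement about specificity, and 118 was not derived for it.

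*The paired power figures are themselves unsourced.* This stands. The documents state no expected gain for TOF alone and no discordance, and independence is an implausible extreme for two reconstructions of one acquisition. A reader might infer that 47% to 90% should replace the stated 90%; it should not.

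**Conclusion.** The concern holds for the specificity conclusion in SAP 2.1 and for nothing wider. A lower limit above 45% supports specificity above 45%, not superiority over an undefined old method in these patients. With 35 benign patients and no true gain, the limit would be met in 31% to 44% of trials if both methods have 60% specificity, and in 77% to 86.5% if both have 70%. With true values of 30% and 50% it would be met in 4.5% to 8.8%, against 31% to 73% for an exact paired test, if the comparator were read in the same patients. All of this rests on assumed true specificities and, for the paired figures, assumed discordance.

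The sample size arithmetic is correct, and the primary AUC comparison is unaffected. The specificity of each image set will be calculated, but without a test or interval for their difference. This should be fixed in the SAP, which is still marked as a draft; it does not invalidate the trial.

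**What to change.** 1. **SAP 2.1.** Define the current method. Keep 45% only as a planning benchmark, with its source if there is one. Delete the sentence that meeting it shows superiority over the old method, and state that the 90% power refers only to exceeding 45%.
2. **SAP 6.1.** Among histologically benign patients, add the paired difference in specificity with versus without TOF, with a 95% confidence interval and an exact McNemar test. Do the same for sensitivity in malignant patients. State in advance one time point and one cut-off rule for both image sets.
3. **Label.** Describe this as a test of the TOF component only.
4. **Power.** Give any paired power only as an illustration, with the assumed gain and discordance beside it.

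**Cost.** No new patients or images are needed. The work goes beyond a 2×2 table, because McNemar needs a binary call from each image set: 6.1 derives the SUVmax cut-off from the trial data and does not say that the PET/CT findings are read separately without TOF. A cut-off rule must therefore be fixed. The sponsor also gives up the use of the 90% as support for a claim against the old method.
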